Permuted block randomization with varying block sizes of 2 and 4 will be used to randomize 100 patients 1:1 to either the intervention or the control group. Random assignment will be conducted using the Statistical Analysis Software (SAS). Given the nature of the intervention, study participants and personnel will not be blinded to group allocation, but data analysts will be.

Intervention

Usual care

At discharge, patients will be provided with a written discharge prescription to be filled at their community pharmacy, and may or may not receive written or verbal instructions about changes made to therapy.

Intervention arm

At discharge, patients (and/or caregivers) will receive access to a medication management application that has been developed by the McGill Clinical and Health Informatics (MCHI) Research Group. The application will retrieve all medications prescribed to patients at discharge from an electronic form with structured data fields that has been completed by a study field coordinator using the patient's discharge prescription. The app will then generate a patient-friendly medication list and will offer a number of important features aimed at addressing barriers to adherence, including:

- **Pill identification:** This feature displays an image of a pill next to each medication in the list, with the intention of ensuring patients take the correct medications at the appropriate dosage and at the right times.
- **Drug information:** Patient-friendly monographs are provided to help patients and caregivers understand the indications for treatment, as well as the harms and benefits of their medications. Improved health literacy with respect to treatment has the potential to increase appropriate utilization of medications by patients.
- **Drug alerts:** Using prescription claims data of the 30 days post-discharge, which will be obtained from the RAMQ, this feature alerts patients to their non-adherence, such as in cases in which they have filled prescriptions that were stopped at hospital discharge, have yet to fill prescriptions for medications newly prescribed at discharge, or have been dispensed medications at the incorrect dose.
- **Daily pill reminders:** This feature reminds patients to take their medication on the day/time they are supposed to. Patients can choose whether or not they want this feature activated.

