- **Weekly dosing schedule:** This feature presents patients with an easy-to-interpret schedule of which medications need to be taken and when (with special instructions, e.g. needs to be taken with food). Medication names are displayed with images of the corresponding pill to prevent mix-ups.
- **Symptom checker:** This feature allows patients to enter their symptoms into the application and

determine which of the medications they are taking has side-effects similar to those they are experiencing.

- **Rate my med:** This feature allows patients to rate the medications they are taking (1-5 stars) and comment on how effective they have been or if they have experienced any negative side-effects. Patients can also view ratings given by other patients using the application for medications they have been prescribed.
- **Caregiver connect:** This feature provides the patient's caregiver(s) with access to their medication lists, as well as notifies them of nonadherence to treatment changes, with the aim of reducing its occurrence. Caregivers will have access to all the same information that patients have access to through the app.
- **Pharmacy connect:** This feature allows patients to connect with their hospital pharmacist and ask any questions they might have regarding their discharge prescription, therapy changes, and drug alerts. Based on their communication with the patient, hospital pharmacists then have the option to (1) recommend a course of action to the patient regarding their medications, (2) consult with the attending physician who was on duty at the time of the patient's discharge regarding a potential change in the patient's prescription, (3) contact the patient's community pharmacist to inform them of any errors in dispensation or any changes made to the patient's prescription, and (4) contact the patient's primary care physician, if and as needed.

Pilot-testing the app

Prior to enrolling patients in the study, we will pilot test the app using data from the RightRx study, which was also conducted in the internal medicine units of the MUHC (study #10-180 GEN). Anonymized data of RightRx patients will be fed into the app to test whether the app appropriately lists prescribed medications and generates the appropriate alerts for nonadherence. This process will help us identify any bugs in the app so that we can fix them prior to the app's use in the pilot trial.

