Once the 30-day follow-up period is complete, patients will retain access to the application for 1 year. The application will still display medications dispensed to patients (obtained through prescription claims data from the RAMQ) to help them keep track of their medications, but adherence alerts will no longer be generated and the pharmacy connect feature will be modified so that patients' messages are faxed to their community pharmacist, who they will be advised to contact regarding any questions they have. Patients/caregivers will also be able to update their medication list manually.

Outcome measures

Usability assessment

Two measures will be used to conduct usability assessment at baseline (i.e. hospital discharge) and during a follow-up visit at 1 week post-discharge. The first, a technology acceptance questionnaire, is a self-administered questionnaire that patients in the intervention group (or their caregivers) will complete and that will assess their satisfaction with the application and collect their feedback on its usability. The second will consist of observing patients (or their caregivers) as they use the app, following the "think aloud protocol".^{8,9} This protocol is widely used to collect data in usability testing¹⁰⁻¹³ and involves users verbalizing their thoughts as they perform a standardized set of tasks, while being audio-recorded. In this project, a study field coordinator who is familiar with the mobile application will observe and record intervention patients (or their caregivers) as they access the app and complete the following standardized tasks: view their medications lists and dosing schedule, peruse drug information, and examine any alerts they might have been issued. Each session will then be transcribed and transcriptions will be qualitatively

analyzed to assess the following usability concepts: the technology's (1) ease of use, (2) user-friendliness, (3) efficiency, and (4) features that may cause confusion, frustration, or user errors.

Patients who complete the home visit at 1 week post-discharge will be provided with a gift card in the amount of \$20 as compensation for their time.

Non-adherence to treatment changes

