The RCT will be conducted at the internal medicine unit of the Royal Victoria and Montreal General sites of the MUHC over a period of 1.5 years (Figure 2). Following approval of the study by the MUHC's institutional review board, study coordinators will begin recruiting, consenting, enrolling, and randomizing eligible patients who are admitted to the internal medicine unit of the MUHC Glen site. Based on recruitment rates from our recently completed trial which was also conducted at the MUHC, we expect this process to take approximately 5-6 months. At discharge, the study coordinator will provide enrolled patients in the intervention arm with access to the mobile application, enter their discharge prescription into the app, acquaint them with and train them in the various features of the app, and conduct a baseline usability assessment.

One week following discharge, study coordinators will conduct usability assessments at patients' homes. Assessment of non-adherence will be conducted by a data analyst at the MCHI Research Group using data from the RAMQ feed and patients' discharge prescriptions. Subsequent data analyses will be conducted over a period of 4 months, beginning 30 days following the enrollment of the last study patient. All data will be stored on a secure server at the MCHI centre, which can only be accessed using employee

identification cards. Following data analysis, an evaluation report will be disseminated to relevant stakeholders at the MUHC (e.g. Committee of Quality and Risk), and a manuscript will be prepared for potential publication in a peer-reviewed journal.

Figure 2. Gantt Chart.

Data storage, privacy, and confidentiality

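### No step carries a prescription change authorised through Pharmacy connect back to the app within the 30 days, so a drug cancelled before its first fill would be flagged, and counted, as non-adherence

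*Combined protocol and SAP*

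**What the plan says.** All references are to the combined protocol and SAP.

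- **Source of the app's list (Intervention arm; Project timeline).** The app takes its medications "from an electronic form with structured data fields that has been completed by a study field coordinator using the patient's discharge prescription". At discharge the coordinator is to "enter their discharge prescription into the app". No later re-entry is described.
- **Drug alerts.** RAMQ claims over 30 days drive the alerts. The examples are patients who have "filled prescriptions that were stopped at hospital discharge, have yet to fill prescriptions for medications newly prescribed at discharge", and patients dispensed a wrong dose.
- **Pharmacy connect.** Patients may "ask any questions they might have regarding their discharge prescription, therapy changes, and drug alerts". Among four options that follow, the hospital pharmacist may "consult with the attending physician who was on duty at the time of the patient's discharge regarding a potential change in the patient's prescription" and may contact the community pharmacist to "inform them of any errors in dispensation or any changes made to the patient's prescription".
- **Caregiver connect.** The feature gives caregivers access and "notifies them of nonadherence to treatment changes, with the aim of reducing its occurrence".
- **After day 30 (last paragraph under Pilot-testing the app; repeated under Data storage, privacy, and confidentiality).** Alerts stop and the link to the hospital pharmacist ends. Manual updating of the list by patients or caregivers is mentioned only here.
- **Outcome (Non-adherence to treatment changes).** Claims for the 30 days are compared with the discharge prescription. The events are a new drug not filled, a stopped prescription refilled, and a dose-modified drug dispensed at the wrong daily dose.

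**The concern.** The intervention contains a route for changing the prescription after discharge, but its alerts are described against the prescription as it stood at discharge. A patient could agree a change with the hospital pharmacist and then receive an alert that contradicts it. The caregiver is notified as well, with the stated purpose of getting the supposed lapse corrected. Under Study population, caregivers of cognitively impaired or fully dependent patients operate the app themselves, so for these patients the wrong message goes to the person managing the drugs. The Background names unclear communication about medication changes as a possible driver of non-adherence, so a contradictory alert works against the app's own purpose.

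The second issue is interpretation. Changes made through Pharmacy connect can occur only in the app arm, and an outcome fixed to the discharge prescription may count them as failures of adherence there.

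**Working it through.** The plan gives no figure to reproduce on this point. The check is to set the rules side by side and apply each one, as worded, to an authorised change.

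**Step 1: do the periods overlap?** Yes. Alerts run for 30 days, and the hospital pharmacist is reachable through the app for the same 30 days. Both arrangements end together.

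**Step 2: does any step update the app in that window?** None is described. The four pharmacist options are advice to the patient, consultation with the attending physician, contact with the community pharmacist, and contact with the primary care physician. None reaches the coordinator or the app. The only list update in the document is the manual one, described for the period after day 30, when alerts have stopped. The pilot test of the alerts uses data from an earlier study and does not mention post-discharge changes.

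**Step 3: apply the rules.**

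| Authorised change | Alert as worded | Outcome as worded |
|---|---|---|
| New drug cancelled before first fill | Would fire: new at discharge, not yet filled | Would count as not filled |
| Stopped drug restarted and filled | Could fire, if matching is by drug and not by prescription | Could count, on the same condition |
| Dose changed after discharge | Could fire, if the unstated reference is the discharge dose | Could count where the dose had been modified at discharge, since claims are compared with the discharge prescription |

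The weekly schedule and the optional reminders would also be out of date if they draw on the same list; their source is not stated.

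**Step 4: does the display of dispensed drugs solve it?** After day 30, "The application will still display medications dispensed to patients", which suggests that dispensed drugs are also shown during the 30 days. A restarted drug would then appear once filled. That does not alter the alert rule, and a cancelled, unfilled drug leaves no claim to display.

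**Step 5: direction and scale for the comparison.** Authorised changes by outside physicians can occur in either arm. Those made through Pharmacy connect occur only in the app arm. Any that are counted, and would not have been events anyway, raise the app-arm mean number of changes not adhered to. With 100 patients randomised 1:1 there are 100/2 = 50 per arm, so one such event adds 1/50 = 0.02 to the app-arm mean and to the difference that the t-test examines. The number of such events is not given and cannot be derived from the documents.

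**The case against.** The strongest reply has five parts.

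- **The wording is not an algorithm.** The alerts are introduced as examples. A drug restarted on a new prescription is arguably not the prescription that was stopped. This stands: only the cancellation case follows from the wording, and the restart and dose cases are conditional. A reader might infer that every authorised change would trigger an alert; the documents do not support that. Nor do they show that the built app lacks an update function, only that none is described.
- **Affected patients are already talking to the pharmacist.** Every Pharmacy connect change begins with the patient's contact, and patients may ask about alerts. This reduces the risk for the patient. It does not correct the alert, and it does not ensure that a separately notified caregiver knows of the change.
- **The study may detect the problem.** At the one-week home visit the coordinator watches users examine their alerts and looks for confusion, and app use is monitored throughout the 30 days. Both may bring a case to light, but neither is tied to a correction.
- **The bias is speculative and conservative.** A reader might infer that the comparison is materially distorted, or try to express the bias as a loss in relative reduction. The documents give neither a rate of such changes nor a control-arm mean, so any percentage would rest on an assumed distribution. The direction is against the app, so this route would not produce a false claim of benefit. An outcome anchored to the discharge prescription also fits the stated aim.
- **Excluding these events is a poor remedy.** Control-arm changes are not logged, so removing authorised changes from the app arm alone would favour the app. It would also reveal allocation to analysts who are meant to be blinded. This stands, and no such comparison is proposed here.

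**Conclusion.** The concern holds in limited form. The alerts and the outcome both refer to the discharge prescription, the plan itself foresees prescription changes in the same 30 days, and it describes no step that brings the two together. A new drug cancelled before its first fill is wrongly flagged and wrongly counted under the rules as written. A restart or a dose change may be, depending on matching rules and a reference dose that the plan does not state.

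The main reason to act is to avoid contradictory medication messages to patients and caregivers. The effect on the comparison is secondary: it runs against the app, it is nil if no such changes occur, and otherwise its size cannot be estimated. The conclusion rests on the alert wording reflecting how the app behaves and on there being no undocumented update process. If one exists, a sentence describing it settles the patient-facing part. Severity is minor; this is a cheap improvement.

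**What to change.** 1. **Carry the change to the app.** When a Pharmacy connect contact results in an authorised change, the pharmacist informs the coordinator, who promptly updates the alert reference and the schedule. The original discharge entry is kept for the outcome. If the entry cannot be edited, the pharmacist tells the patient and the caregiver which alert to disregard.
2. **State the rules.** Say whether stopped drugs are matched by drug or by prescription, which dose the dose alert refers to, and where the schedule and reminders take their content.
3. **Log and report.** Keep a dated log of these changes, held away from the analysts until the blinded main analysis is finished. Leave the main outcome as defined. Afterwards, report descriptively how many app-arm events were authorised Pharmacy connect changes.

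The cost is one protocol paragraph, a little staff time and possibly minor programming before enrolment, since the documents do not confirm that the entry can be edited. Changes by outside physicians will be caught only if someone reports them, so some wrong alerts will remain.

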Pharmacy claims data from the RAMQ will be used to identify community medications dispensed to participating patients in the 30 days following hospital discharge. These data will be compared with the patient's hospital discharge prescription to identify non-adherence to in-hospital medication changes. Non-adherence to in-hospital treatment changes in the 30-day post-discharge period will be defined as (1) failure to fill newly prescribed medications, (2) re-filling a previous prescription that was stopped at discharge, or (3) filling a previous prescription whose dosage was modified at discharge, but was dispensed post-discharge at the incorrect daily dose.

Data sources

Prescription claims data from the *Régie de l'assurance maladie du Québec (RAMQ)* will be used to identify prescriptions filled in the 3 months prior to admission and the 1 year following discharge.

Medications prescribed at discharge and in-hospital medication changes will be determined using patients' discharge prescriptions, which will be obtained from patients' hospital charts.

Data Analysis

Descriptive statistics will be used to summarize demographic and clinical characteristics of the study population, results of the technology assessment questionnaire, and the frequency of nonadherence events (as defined in the previous section) in the 30 days post-discharge, overall and in each study group. We will then compare, between intervention and control groups, the average number of in-hospital medication changes not adhered to in the 30-day follow-up period using the Student's t-test. All quantitative statistical analyses will be conducted using SAS version 9.4. Data from the "think aloud" protocol will be analyzed qualitatively.

[figure not shown]
Project timeline

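### Do coordinator training and observed app sessions, given only to the intervention arm, undermine the 30-day comparison of non-adherence?

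*Combined protocol and SAP*

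**What the plan says.** The Methodology section randomises 100 patients 1:1 to access to the app or to usual care without medication management support. The same paragraph announces usability assessments at discharge and at one week.

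Project timeline sets out what happens at discharge: "the study coordinator will provide enrolled patients in the intervention arm with access to the mobile application", enter the discharge prescription, "acquaint them with and train them in the various features of the app, and conduct a baseline usability assessment". It continues: "One week following discharge, study coordinators will conduct usability assessments", at patients' homes. That last sentence names no arm, but Usability assessment supplies it: the coordinator "will observe and record intervention patients (or their caregivers) as they access the app and complete the following standardized tasks". The tasks cover the medication list and dosing schedule, and users also "peruse drug information, and examine any alerts they might have been issued". Attendance is compensated: "Patients who complete the home visit at 1 week post-discharge will be provided with a gift card".

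The alerts are generated "Using prescription claims data of the 30 days post-discharge". They concern stopped drugs that were refilled, new drugs not yet filled, and drugs dispensed at an incorrect dose. The outcome section defines non-adherence by the same three kinds of event, the first being "failure to fill newly prescribed medications". Data Analysis then has one between-arm test, a Student's t-test on the mean number of medication changes not adhered to over 30 days.

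The section on recruitment, consent and enrollment describes an app demonstration to the patient and a chosen caregiver, and an e-mailed access link for a caregiver absent at discharge. Neither step names an arm. Data storage, privacy, and confidentiality likewise creates an account for every enrolled patient.

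**The concern.** If the intervention is read as access to the app and nothing else, the intervention arm receives more than that. A coordinator trains these patients and twice watches them use the app. The second session falls inside the outcome window and asks them to look at alerts about the very events being counted. A patient who opens an alert with a coordinator present and then fills a new prescription has one non-adherence event fewer, and the t-test cannot separate that from what the app would have achieved alone. Blinded analysts and claims-based outcome data guard against biased ascertainment, but not against an effect of contact on behaviour. A hospital reader could then credit access alone with a benefit that partly came from a home visit.

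The enrolment wording raises the opposite worry. Taken literally, a control patient with a caregiver might be shown the app or a caregiver sent the link, which would dilute the difference.

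**Working it through.** The protocol states no significance level, power, effect size or standard deviation, so there is no figure of its own to reproduce. The check is mainly a comparison of sections.

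**Who gets what, and when**

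| Contact | Section | Arm | Time |
|---|---|---|---|
| App access, prescription entry, training | Project timeline | Intervention | Discharge |
| First observed session | Usability assessment; Project timeline | Intervention | Discharge |
| Second observed session, at home | Usability assessment; Project timeline | Intervention | About day 7 |
| Matching contact for controls | None described | – | – |

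**Extent**

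- Patients per arm: 100 / 2 = 50, so at most about 50 home sessions in the intervention arm and none described in the control arm.
- Window left after the visit: 30 − 7 = 23 days, and 23 / 30 = 77%.
- Alerts rest on post-discharge claims, so none is expected at the discharge session. The home session is the one at which alerts could be opened.

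These figures describe the schedule, not an effect. Nor does counting outcome types help. An unfilled new prescription is the event an alert can most clearly still reverse, but viewing the list and schedule could also prevent a later refill or dose error. The share of the outcome open to influence is unknown.

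**How much could contact alone do?** This is an illustration under assumptions that are not in the protocol: 50 per arm, two-sided alpha 0.05, normal approximation, app access alone having no effect, and contact shifting the mean by d standard deviations.

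- Standard error of the difference: √(2/50) = 0.20 SD.
- Probability of significance: Φ(d/0.20 − 1.96) + Φ(−d/0.20 − 1.96).

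| d (SD) | 0.1 | 0.2 | 0.3 | 0.4 | 0.5 |
|---|---|---|---|---|---|
| Probability | 8% | 17% | 32% | 52% | 71% |

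The difference detectable with 80% power is (1.960 + 0.842) × 0.20 = 0.56 SD. The table spans nearly the whole range from negligible to important because d is unknown. It is not evidence that the contact effect is large.

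**What does the analysis claim?** Data Analysis compares the intervention and control groups. It does not say that the difference isolates access. Randomisation makes it a valid estimate of everything the intervention arm receives against usual care.

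**Would another design gain anything?**

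- *Matched visits for controls.* Controls have no app to be observed using. A visit spent going over their medications would itself be support, contrary to the control arm's definition.
- *Moving the session beyond day 30.* Just before Outcome measures, the protocol says that adherence alerts stop after 30 days and the pharmacy link changes. A later session would test a different app and lose early feedback.
- *Observing only a subset.* This would reduce the contact but also the usability data, which are half of the objective.

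**Enrolment wording.** The caregiver's undertaking to use the app and be assessed is an agreement required before entry, so it is naturally the same for both arms. That leaves the demonstration, the e-mailed link and the account. Methodology, Intervention arm, Usability assessment and Project timeline together reserve access, training and assessment for the intervention arm. No section plans to give controls the app.

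**The case for a change.** The strongest argument for a change is that the home session is a research procedure that would not accompany the app in routine use. It directs patients to alerts about the endpoint and occurs with most of the window still to run. One sentence in Data Analysis naming training and sessions as part of the comparison would cost nothing. On enrolment, the demonstration is described during enrolment, and Project timeline lists enrolling before randomising, so a coordinator could show the app before allocation is known.

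Part of this stands. The result is the effect of the app as delivered in this trial, including the observed sessions, and the report should describe it so. The arm for the demonstration, link and account could also be stated more clearly. But the first is a matter of describing procedures already set out openly, and it leaves the data, test, visits and sample size as they are. The second is a gap that the other sections fill. Dilution would require staff to follow the enrolment section while disregarding Project timeline, which assigns access and training to the intervention arm.

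**Conclusion.** The observations are accurate, but no change to the plan follows. The unequal contact is a fair trade-off in a trial that sets out to study usability and efficacy together, and training belongs to delivering the app. The one clearly research-driven element is the home session: up to about 50 sessions at about day 7, with about 23 of 30 days remaining. The between-arm test stays valid for the app as delivered versus usual care. The arm-neutral enrolment and account wording is a clerical gap.

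This rests on two readings: that the efficacy conclusion will be worded for the app as delivered, since Data Analysis claims nothing narrower, and that staff follow the sections that assign access and training to the intervention arm. Neither a contact effect nor any exposure of controls can be sized from the documents; the 8% to 71% range depends wholly on assumed shifts.

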We will conduct an RCT that will assess the usability of a medication management mobile application and its efficacy in decreasing non-adherence to in-hospital medication changes among patients in the internal medicine ward of the Royal Victoria and Montreal General sites of the MUHC. One hundred patients will be randomized 1:1 to either the intervention arm, in which they will receive access to the mobile app, or the control arm, in which they will receive usual care (i.e., no medication management support). We will conduct a usability assessment at hospital discharge (baseline) and at 1 week post-discharge to obtain patient feedback on the app (via a technology acceptance questionnaire) and to document usability using the “think aloud” protocol^{8,9}. We will also compare, between the 2 arms, the rates of non-adherence to treatment changes in the 30-days post-discharge.

Study population

The study population will comprise 100 patients who are discharged from the internal medicine unit of the Royal Victoria and Montreal General sites of the MUHC. To be eligible for participation in the trial, patients must also be covered by the Quebec public insurance drug plan (i.e. they are 65 years or older, are recipients of social assistance, or do not have private drug insurance), must be 18 years or older at the time of admission, must own a tablet, smartphone, desktop PC, or portable computer, must have internet connection on their tablet/smartphone/laptop/PC, must speak and read either English or French, must not be discharged to a rehabilitation or long-term care center, and must have a prognosis of more than 3 months.

Patients who are cognitively impaired or otherwise unable to provide consent will be eligible for inclusion in the study if surrogate consent is granted by a legally authorized representative and if a caregiver has agreed to use the app on the patient’s behalf. Similarly, patients who are completely dependent on a caregiver but capable of providing consent will be enrolled only if the caregiver has agreed to use the app.

Participant recruitment, consent, and enrollment

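### Filling is judged only from public-plan claims, so a new drug that cannot generate a claim is scored as non-adherence whatever the patient does

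*Combined protocol and SAP*

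**What the plan says.** All references are to the combined protocol and SAP.

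- **Outcome measures, Non-adherence to treatment changes.** Dispensing has one source: "Pharmacy claims data from the RAMQ will be used to identify community medications dispensed to participating patients" in the 30 days after discharge. The claims are compared with the discharge prescription. The first of three event types is "failure to fill newly prescribed medications". No type of drug is set apart.
- **Data sources.** "Medications prescribed at discharge and in-hospital medication changes will be determined using" the discharge prescriptions held in the hospital charts. Coverage of the individual drug plays no part.
- **Project timeline.** "Assessment of non-adherence will be conducted by a data analyst at the MCHI Research Group using data from the RAMQ feed" together with the discharge prescriptions. No other source is named.
- **Study population.** Patients must be "covered by the Quebec public insurance drug plan".
- **Intervention arm, Drug alerts.** The same claims drive an alert to patients who "have yet to fill prescriptions for medications newly prescribed at discharge".
- **Data Analysis.** Event frequencies are described overall and by arm. The mean number of changes not adhered to is then compared by Student's t-test.

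**The concern.** A claims file holds only what was claimed. When it is the sole evidence of filling, no claim has to be read as not filled. For a drug that can be claimed, that is a reasonable reading. For a drug that cannot, the score is fixed before the patient does anything: one event, in either arm, whether or not the drug was obtained.

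Three things are at stake. The described frequency of non-adherence would be too high. The count entering the t-test would carry variance that has nothing to do with behaviour, in a trial of 100 patients. And in the intervention arm, the alert built on the same claims could tell a patient who has the drug that it is still unfilled.

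**Working it through.** **Reading the rule.** The plan does not write out that no claim means not filled, but the two inputs allow no other scoring. I looked for a safeguard in three places.

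- Eligibility covers the person, not each item on the prescription.
- Manual updating of the medication list is described for the period after the 30 days, and is not an outcome source.
- The pilot test checks the app's lists and alerts on data from an earlier study. It does not test the outcome definition.

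**Effect on the comparison.** Let an arm have true mean μ, and let each patient have m new drugs, each non-claimable with probability q and always scored as an event.

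- Observed mean = μ + qm in each arm. The term qm cancels in the difference.
- Observed variance = true variance + mq(1 − q). This does not cancel.

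**Illustration of size.** The plan gives no mean count, SD, effect size, alpha or power, so there is no figure of its own to reproduce.

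From the documents:
- 50 per arm (100 patients, 1:1);
- 54% of earlier patients non-adherent to at least one change (Background).

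Assumed:
- q = 5–20% and m = 2–3;
- every non-claimable drug is in fact obtained;
- a true 50% reduction;
- two-sided alpha 0.05;
- the shape of the count.

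*Poisson count.* Control mean = −ln(1 − 0.54) = 0.777; intervention 0.388; difference 0.388. Average variance = (0.777 + 0.388)/2 = 0.582.

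*Overdispersed count (negative binomial, k = 1, matched to the same 54%).* Control mean = 1/0.46 − 1 = 1.174; intervention 0.587; difference 0.587. With variance μ + μ², the average is (2.552 + 0.931)/2 = 1.742.

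The second shape matters because Background reports a risk for patients with 4 or more changes not adhered to. The Poisson puts only 0.8% of patients there; the negative binomial puts 8.5%.

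Power is from simulation of the t-test (40,000 runs). The control share with at least one event is 1 − 0.46(1 − q)^m.

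| q, m | False events per patient (qm) | Control with ≥1 event | Power, Poisson | Power, neg. binomial |
|---|---|---|---|---|
| none | 0 | 54% | 72% | 61% |
| 5%, 2 | 0.10 | 58% | 66% | 59% |
| 10%, 2 | 0.20 | 63% | 60% | 57% |
| 10%, 3 | 0.30 | 66% | 55% | 55% |
| 20%, 3 | 0.60 | 76% | 46% | 50% |

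Other simulation runs give 65% for the second Poisson row, and 62% falling to 58–50% for the negative binomial. Nothing rests on a difference of a point.

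Hand check by Φ(difference/SE − 1.96), with SE = √(2 × variance/50):
- Poisson, no false events: 0.388/√(2 × 0.582/50) = 2.54, so power is Φ(0.58) = 72%.
- Poisson, q = 20% and m = 3: variance = 0.582 + 3 × 0.2 × 0.8 = 1.062; 0.388/0.206 = 1.88, so power is Φ(−0.08) = 47%.

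**The case against.** **The comparison is not biased.** This stands. A reader might infer that the treatment effect itself is distorted. The planned analysis is a difference in mean counts, and false events expected equally in both arms cancel from it. A relative reduction would be diluted, but the plan proposes none.

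**The size is guesswork.** This also stands. Neither the share of non-claimable drugs nor the number of new drugs per patient is in the documents. The false load is an upper bound for a given q and m, since it assumes every such drug was obtained. If the earlier 54% came from a similar claims rule, it may already contain false events, and adding more would count them twice. Under overdispersion the loss of power is smaller. No power target is stated, and the plan itself calls the study a pilot at one point. The power figures therefore show a possible order of size and are not a finding about this trial.

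**As-needed drugs.** A reader might extend the point to as-needed drugs that were never needed. The documents do not support that. A reimbursed as-needed drug can generate a claim, and not filling it meets the stated definition. Excluding it would replace filling with need as the thing measured.

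**Existing safeguards.** The pilot test of alerts, and the feature that lets patients question alerts with the hospital pharmacist, are partial protection for the alert. Neither touches outcome scoring.

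**Conclusion.** The point holds as a flaw in the outcome rule: for a new drug that cannot generate a RAMQ claim, the rule returns an event regardless of behaviour. The consequences are an inflated reported frequency, added variance in the t-test, and possibly false alerts in the intervention arm. The expected difference in means is unaffected.

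The size is unknown. Under the assumed inputs, the loss of power runs from a few points to about 26 (Poisson, 72% to 46%) or about 12 (overdispersed, about 62% to 50%). If no discharge drug falls outside claims, nothing changes. The change is worth making because the gap is clear in the text and cheap to close, not because a large loss has been shown.

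**What to change.** In the outcome definition, limit the failure-to-fill component to newly prescribed drugs that can generate a RAMQ claim for that patient. Have an analyst blind to arm classify the drugs from the discharge prescription before claims are examined. Report the number excluded by arm, and give the count over all new drugs as a sensitivity analysis. Leave as-needed drugs under the same rule as any other. Make the claims-based definition behind the unfilled-prescription alert consistent with the outcome definition.

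The cost is a sentence or two in the protocol and a drug-list lookup, with no new patients or data collection. The downside is that genuine non-filling of non-claimable drugs leaves the main count. Today it is counted, but it cannot be told apart from a purchase made without a claim. The sensitivity analysis keeps it visible.
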